### **3.3 Replacement of Subjects**

- If a subject is withdrawn from the study before week 8 for reasons not related to toxicity of study drug, the subject will be replaced.
- If a subject does not take at least 12 of the intended 16 doses in the first 8 weeks, the subject will be replaced because he/she has not taken enough THU-Dec that analysis of the primary end-point will be meaningful.

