### 3.0 STUDY DESIGN

**3.1 Study design:** This is a Phase 2 randomized two arm trial of nivolumab alone or in combination with THU-Dec, in previously treated patients with stage IV Non-Small Cell Lung Cancer (NSCLC). The primary goal of this trial is to compare the efficacy of oral THU-Dec as a way of enhancing the anti-tumor immune response to nivolumab to that of nivolumab alone. The primary efficacy endpoint is overall RECIST v1.1-defined response. To accomplish this goal 60 patients will be randomized 2:1 to THU-Dec plus nivolumab or nivolumab only respectively.

**3.2 Statistics and Sample size justification:** The primary goal of this trial is to compare the efficacy of immune priming with oral tetrahydrouridine (THU) plus decitabine (THU-Dec) and immune check-point inhibitor nivolumab (THU-Dec+nivolumab) to that of nivolumab alone. The primary efficacy endpoint is overall response. To accomplish this goal 60 patients will be randomized 2:1 to THU-Dec+nivolumab versus nivolumab alone (standard of care) respectively. The purpose of the nivolumab alone arm is to support the notion that the population studied is typical of the general population for which nivolumab has an established response rate of 20%. If the THU-Dec+nivolumab arm has a response rate of 35% or higher, we will consider it worthy of further investigation in a phase III trial. Thus, using a two-stage design (<http://www.swogstat.org/stat/public/twostage.htm>), with  $\alpha = 0.1$  and  $\beta = 0.2$ , we compute that 20 patients will be needed in each of two stages in the THU-Dec+nivolumab arm. If, after the 1st stage of 20 patients in the THU-Dec+nivolumab arm, 2 or fewer respond, the trial will be stopped and the null hypothesis that THU-Dec+nivolumab is no better than nivolumab will be accepted, else the trial continues for an additional 20 patients, at the end of which if 13 or more respond of the 40

patients in the THU-Dec+nivolumab arm, the null hypothesis is rejected and experimental arm of THU-Dec+nivolumab is recommended for further study.

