**- Frequency of THU and Dec ingestion:**

Oral THU ~10 mg/kg is administered 60 minutes before oral decitabine ~0.2 mg/kg 2X/week on consecutive days if there is no  $\geq$  grade 3 treatment-related non-hematologic toxicity and the ANC is  $>0.5 \times 10^9/L$  (if ANC is  $<0.5 \times 10^9/L$ , treatment is held until recovery above this threshold then resumed with a dose reduction as per Table 1).

- Patients will be required to have the treatment on the same consecutive days every week. If patients miss a dose they need they can make up the dose the same week ( $\pm 3$  days) and the study team needs to be notified.

- G-CSF neutropenia prophylaxis is recommended 1X/week if the ANC is  $<1.5 \times 10^9/L$

**If there is stable disease or partial response by RECIST v1.1 at the week 8 or 16 staging CTs, and there are no treatment-related  $\geq$  grade 3 toxicities, and blood count trends (trends in the absolute neutrophil, absolute lymphocyte and platelet counts) suggest that such treatment-related toxicities are not imminent, the dose of THU and Dec can be increased by one capsule each. THU-Dec dose increases should not occur**

more often than every 4 weeks and only to a maximum of 2 additional capsules of each drug from the starting dosage.

-Pre-medications are not required, since nausea, vomiting and diarrhea are not anticipated with this non-cytotoxic mode of therapy.

Dose modifications (dose reductions, dose escalations) of oral THU-Dec are described in Section 7.0

Reported adverse events and potential risks of oral THU-Dec are described in Section 8.0

No investigational or commercial agents or therapies other than those described below may be administered with the intent to treat the subject's malignancy.

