### **6.3 General Concomitant Medications**

The following medications are prohibited during the study (unless utilized to treat a drug-related adverse event):

- a) Immunosuppressive agents
- b) Immunosuppressive doses of systemic corticosteroids
  - Any concurrent antineoplastic therapy (ie, chemotherapy, hormonal therapy, immunotherapy, extensive radiation therapy, or standard or investigational agents for treatment of NSCLC Palliative and supportive care for disease related symptoms may be offered to all subjects on the trial. Palliative (limited-field) radiation therapy is permitted for subjects who have investigator assessed clinical benefit. However, radiation to target lesions is not permitted. For example patients with asymptomatic oligo-metastatic brain metastatic disease that would clinically be amenable to Gamma Knife Radiosurgery is allowed on the protocol so long as they are not having systemic disease progression and per investigator are receiving clinical benefit from the trial.
  - Inter-current illness that prevents further administration of treatment
  - The investigator considers it, for safety reasons, to be in the best interest of the subject
  - Unacceptable treatment related toxicity, NCI CTC AE version 4.0 Grade 3 or 4 that fails to recover to baseline or < Grade 3 in the absence of treatment within 4 weeks See section 6.1.1, 6.1.2 and 6.1.3.
  - Subject decision to withdraw from treatment (partial consent) or from the study (full consent)
  - Pregnancy during the course of the study for a child-bearing participant
  - Death, or
  - Sponsor reserves the right to temporarily suspend or prematurely discontinue this study.
  - The date and reason for discontinuation must be documented. Every effort should be made to complete the appropriate assessments

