### **6.5 Stopping Rule**

If 3 of the first 5 patients in the THU-Dec + nivolumab arm are removed from study for grade 3/4 non-hematologic toxicity or toxicities prior to cycle 2 that are likely attributable to THU-Dec, the study will be terminated.

The study incorporates a two-stage design in the experimental THU-Dec + nivolumab arm. If after the 1st stage of 20 patients in the THU-Dec+nivolumab arm, 2 or fewer respond, the trial will be stopped and the null hypothesis that THU-Dec+nivolumab is no better than nivolumab will be accepted, else the trial continues for an additional 20 patients.

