### **6.6 Duration of Follow Up**

Subjects will be followed for toxicity for 30 days after treatment has been discontinued, until start of new anti-cancer treatment or until death, whichever occurs first. The clinical course of each event will be followed until resolution, stabilization, or until it has been determined that the study treatment or participation is not the cause, unless the event exceeds 6 months in duration. Serious adverse events that are still ongoing at the end of the study period will necessitate follow-up to determine the final outcome. Any serious adverse event that occurs after the study period and is considered to be possibly related to the study treatment or study participation will be recorded and reported immediately. All randomized subjects who discontinue study treatment must continue to be followed for collection of outcome and/or survival follow-up data every 2 months until death or subjects withdraw consent from all study related activities. The survival and toxicity follow up of the patients could be by telephone or through review of medical records.

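### Section 3.3 replaces under-dosed THU-Dec subjects as uninformative for the primary end-point, section 12.1 counts everyone randomized, and no cut-off exists once replacement takes the arm above 40

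*Combined protocol and SAP*

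**What the plan says.** Section 3.3 has two replacement rules. The first covers a subject "withdrawn from the study before week 8 for reasons not related to toxicity of study drug, the subject will be replaced". The second reads: "If a subject does not take at least 12 of the intended 16 doses in the first 8 weeks, the subject will be replaced". The reason given for the second is that the subject "has not taken enough THU-Dec that analysis of the primary end-point will be meaningful".

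The decision rules in sections 3.2 and 6.5 concern the THU-Dec plus nivolumab arm. After 20 patients, if "2 or fewer respond, the trial will be stopped and the null hypothesis that THU-Dec+nivolumab is no better than nivolumab will be accepted". Otherwise section 3.2 says "else the trial continues for an additional 20 patients, at the end of which if 13 or more respond of the 40", the null hypothesis is rejected. Section 3.2 states a 20% null rate, a 35% target rate, alpha 0.1 and beta 0.2. It plans 60 patients at 2:1, which is exactly 40 plus 20 with no allowance for replacements.

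Section 12.1 defines the objective response rate with everyone randomized in the denominator. The closing paragraph of section 12.2 puts all consented, randomized and registered subjects in the primary efficacy dataset.

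**The concern.** The go/no-go decision is a count out of 20 followed by a count out of 40. The reason in section 3.3 suggests that under-dosed subjects do not belong in those counts; sections 12.1 and 12.2 say that they do.

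- **If they are left out,** the 40 are selected after randomization on early tolerance and adherence, and a documented responder with 11 doses is lost. Low dosing need not be a matter of choice. Table 1 in section 7.1 holds THU-Dec for toxicity and can reduce its frequency, and the second rule in 3.3, unlike the first, makes no exception for toxicity.
- **If they are kept,** every replacement takes the arm above 40, where the plan has no cut-off. It also does not say whether stage 1 is the first 20 randomized or the first 20 with enough doses.

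Either way, the choice could be made after the responses are known.

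**Working it through.** **Inputs.** From section 3.2: null rate 0.20, target rate 0.35, stop at 2 or fewer of 20, go at 13 or more of 40, alpha 0.10, power 0.80. The documents give neither the number replaced nor their response rate, so both are assumptions here.

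**Formula.** With stage 1 fixed at 20, final size N (treated as fixed), cut-off c and response rate p:

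P(go) = sum over x = 3 to 20 of Bin(x; 20, p) × P[Bin(N − 20, p) ≥ c − x]

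**Step 1: the plan's own design.**

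| Rule at N=40 | P(go) at 20% | P(go) at 35% |
|---|---|---|
| 13 of 40, as written | 0.043 | 0.685 |
| 12 of 40 | 0.087 | 0.793 |

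The written cut-off does not reproduce the stated 0.10 and 0.80; a cut-off of 12 comes close. This affects how much room there is for replacements.

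**Step 2: replaced subjects kept, cut-off still 13.**

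| N | alpha | power at 35% |
|---|---|---|
| 41 | 0.052 | 0.723 |
| 42 | 0.062 | 0.758 |
| 43 | 0.073 | 0.789 |
| 44 | 0.085 | 0.818 |
| 45 | 0.099 | 0.843 |
| 46 | 0.113 | 0.865 |
| 50 | 0.182 | 0.928 |

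The stated 0.10 is passed at the sixth replacement. If 12 were the intended cut-off, carrying it to N=41 already gives 0.1015.

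**Step 3: replaced subjects left out, 13 of 40 retained.** Suppose the rate among all randomized is 20%, a fraction f is replaced, and replaced subjects respond at rate q. The retained rate is (0.20 − f·q)/(1 − f).

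| f | q | retained rate | false go |
|---|---|---|---|
| 10% | 0 | 0.222 | 0.088 |
| 20% | 0 | 0.250 | 0.179 |
| 10% | 10% | 0.211 | 0.063 |
| 20% | 10% | 0.225 | 0.096 |
| any | 20% | 0.200 | 0.043 |

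By count with q = 0, five replaced of 45 gives a retained rate of 0.20 × 45/40 = 0.225 and false go 0.096. Six of 46 gives 0.230 and 0.110.

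**Step 4: how often the two readings would decide differently.** This applies cut-off 13 to both. If replaced subjects respond like the others, 1, 3 or 5 replacements give opposite decisions in 0.9%, 3.0% or 5.6% of simulated trials at a 20% rate, and in 3.8%, 10.5% or 16.0% at 35% (200,000 trials per case). If replaced subjects never respond, the readings differ in at most 0.3% of trials for up to five replacements.

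**The case against.** The strongest reply is that sections 12.1 and 12.2 already name the analysis set, and that 3.3 is an accrual rule with an ill-chosen reason. Section 3.3 nowhere says that a replaced subject is removed from analysis. This largely stands: keeping replaced subjects is the better-supported reading. It does not supply a cut-off above 40 or a definition of stage 1, and the reason in 3.3 still contradicts it.

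A second reply is that the effect is small. A subject must finally lack at least five of 16 doses, and section 6.2 allows catching up: "If patients miss a dose they need they can make up the dose the same week". With up to five replacements neither reading exceeds 0.10. This stands too, but only if 13 of 40 is intended.

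The two harms of exclusion also do not peak together. False-go inflation is largest when replaced subjects never respond, and then the readings almost always agree. Disagreement is sizeable when they respond like the others, and then exclusion leaves alpha at 0.043.

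A reader might infer more than the documents support:

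- **That 13 responders among 41, one of them replaced, is a go on one reading and a failure at 12 of 40 on the other.** This assumes that 13 applies at N=41, which the plan does not say.
- **That the first rule in 3.3 replaces early progressors and deaths.** The discontinuation list printed under section 6.3 separates the two kinds of withdrawal ("Subject decision to withdraw from treatment (partial consent) or from the study (full consent") and lists death as its own item. Section 6.6 adds: "All randomized subjects who discontinue study treatment must continue to be followed for collection of outcome and/or survival follow-up data". The first rule therefore most likely means leaving the study altogether.

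**Conclusion.** The conflict between 3.3 and 12.1/12.2 is in the text, and the gap above 40 remains on the better-supported reading. It should be fixed, but it does not by itself invalidate the design. A reader might conclude that the plan discards under-dosed patients or that its error rate is already broken. The documents establish neither: exclusion is inferred only from the reason in 3.3, and the 10% and 20% replacement rates are assumptions.

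Keeping everyone at cut-off 13, alpha is 0.099 at N=45 and 0.113 at N=46. Excluding replaced subjects, the matching worst cases are 0.096 and 0.110, with no responders among those replaced and a 20% rate among all randomized. The room for five replacements exists only because 13 of 40 is stricter than the stated alpha. With 12 as the cut-off, one replacement uses it up.

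**What to change.** Reconcile sections 3.2, 3.3, 6.5 and 12.1 with one rule:

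1. Settle the cut-off at N=40 first, because 13 does not match the stated alpha and beta.
2. All subjects randomized to THU-Dec count in the primary decision, whatever the doses taken. Anyone without a documented RECIST v1.1 response is a non-responder.
3. Stage 1 is the first 20 randomized to THU-Dec.
4. Pre-specify the final cut-off by N. With 13 at N=40, use 13 for N=41–45 (alpha at most 0.099), 14 for N=46–49 (0.061 to 0.096) and 15 for N=50–53 (0.060 to 0.092). These are the smallest cut-offs that hold alpha at 0.10.
5. Report subjects with at least 12 of 16 doses as a supportive analysis only, and delete the reason that 3.3 gives for its second rule.

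**Cost.** The plan does not say whether 35% refers to adequately dosed patients only. If it does, and replaced subjects do not respond, the rate among all randomized is 0.35 × 40/N. Power is then about 0.68 at N=45 (cut-off 13), 0.55 at N=46 (cut-off 14) and 0.43 at N=50 (cut-off 15). Enrolment also exceeds 60 by the number replaced.

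**Alternative.** Apply both rules to the first 20 and first 40 randomized, so that replacements do not enter the primary decision. The possible power loss is larger. With 10% or 20% non-responding drop-out the rate is 0.315 or 0.28, power falls from 0.685 to 0.50 or 0.32, and the chance of a stage 1 stop rises from 0.012 to 0.026 or 0.053. This is a design trade-off for the sponsor to settle before the stage 1 count.

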### **3.4 Expected Duration of Treatment and Subject Participation**

Treatment on protocol monitoring continues until (i) disease progression (defined by RECIST v1.1 with the following caveat: since it is known that there can be initial progression by RECIST v1.1 criteria with immune checkpoint blockade followed by subsequent regression and clinical benefit, if the treating clinical team and the patient judge that they have benefitted from therapy, treatment continuation is allowed even if there is disease progression by RECIST v1.1 criteria. However, patients should have confirmed stable disease or better at the time of the following scheduled imaging time-point. If there

is progression at this following re-staging, patients should be discontinued from therapy); (ii) toxicity as defined in Section 7.1; or (iii) withdrawal of consent up to a maximum of 24 months.

At the end of the protocol-specified period of active study therapy, the sponsor will not continue to supply study drug to subjects/investigators unless the sponsor chooses to extend the study, which may include continuation of nivolumab. The investigator should ensure that the subject receives appropriate standard of care, which may include continued treatment with nivolumab.

#### **4.0 SUBJECT SELECTION**

Each of the criteria in the sections that follow must be met in order for a subject to be considered eligible for this study. Use the eligibility criteria to confirm a subject's eligibility.

##### **4.1 Inclusion Criteria**

Patients must meet all of the following inclusion criteria to be eligible for enrollment into the study:

1. Histologically or cytologically-proven NSCLC
2. Subjects must have received 1 or more prior systemic therapies for this disease, (this can include neo-adjuvant or adjuvant chemotherapy if administered <2years prior to study enrollment), should not have had prior treatment with immunotherapy (including immune checkpoint inhibitor drugs, or immunotherapy vaccines); Patients with EGFR or ALK alterations will need to have progressed on a TKI treatment.
3. Measurable disease per RECIST v1.1
4. Disease that can be accessed by a bronchoscopic, surgical or percutaneous biopsy, eligible for biopsy from safety perspective, and agrees to biopsy prior to study. The pre-study biopsy can be waived if (i) there is an archival biopsy specimen that was obtained after the most recent therapy or(ii) if the risks of biopsy are judged to be excessive by the study PI
5. ECOG performance status 0 – 2
6. Male or female, 18 years or older (Because no dosing or adverse event data are currently available on the use of oral THU-Dec in subjects ≤18 years of age, children are excluded from this study)
7. Adequate organ function as defined by the following criteria:

##### **Adequate Organ Function Laboratory Values**

System	Laboratory Value
---------------	-------------------------

Hematological	
Absolute neutrophil count (ANC)	$\geq 1,500$ /mcL
Platelets	$\geq 100,000$ / mcL
Hemoglobin	$\geq 8.5$ g/dL or $\geq 5.6$ mmol/L
Renal	
Serum creatinine OR Measured or calculated a creatinine clearance	$\leq 1.5$ X upper limit of normal (ULN) OR  $\geq 30$ mL/min for subject with creatinine levels > 1.5 X institutional ULN
Hepatic	
Serum total bilirubin	$\leq 1.5$ X ULN OR
	Direct bilirubin $\leq$ ULN for subjects with total bilirubin levels > 1.5 ULN
AST (SGOT) and ALT (SGPT)	$\leq 2.5$ X ULN OR $\leq 5$ X ULN for subjects with liver metastases
Albumin	$\geq 2$ mg/dL
a Creatinine clearance should be calculated per institutional standard.	

8. Patients with leptomenigeal disease are not eligible but patients with brain metastases are eligible – these patients should commence treatment on study > 1 week after completion of gamma knife or whole brain radiotherapy or >4 weeks after surgical resection of brain metastasis. Patients should ideally be off steroids at the start of study treatment, however patients on steroid taper and a dose of no more than 2mg/day of dexamethasone can begin study treatment; and steroids should be tapered off as quickly as clinically feasible. Repeat brain MRI after radiation is not required for eligibility but is strongly recommended, to establish the pre-treatment baseline status of any brain metastases, necessary to accurately assess for response or progression.

Patients with untreated, asymptomatic brain metastasis not requiring steroids are also eligible, however, these patients need to be discussed with the study PI prior to being registered.

9. Subjects must have the ability to understand and the willingness to sign a written informed consent document.

## 4.2 Exclusion Criteria

The presence of any of the following will exclude a patient from study enrollment:

1. Within 6 months prior to study drug administration, clinically significant cardiovascular/cerebrovascular disease defined as follows: cerebral vascular accident/stroke, myocardial infarction, unstable angina, congestive heart failure (New York Heart Association Classification Class  $\geq$  II), bleeding or pulmonary embolism or cardiac arrhythmias that was severe enough to cause hemodynamic compromise.
2. Known human immunodeficiency virus (HIV) or acquired immunodeficiency syndrome (AIDS)-related illness (HIV-positive subjects on combination antiretroviral therapy are ineligible because of the potential for pharmacokinetic interactions with oral THU-Dec. Appropriate studies will be undertaken in subjects receiving combination antiretroviral therapy when indicated.
3. Pregnancy or breastfeeding (pregnant or breastfeeding women are excluded from this study because oral THU-Dec has the potential for teratogenic or abortifacient effects. Because there is an unknown, but potential risk for adverse events in nursing infants secondary to treatment of the mother with oral THU-Dec, breastfeeding should be discontinued if the mother is treated with oral THU-Dec.
4. Other severe acute or chronic medical or psychiatric conditions or laboratory abnormality that may increase the risk associated with study participation or study drug administration, or may interfere with the interpretation of study results, and in the judgment of the investigator would make the patient inappropriate for entry into this study.
5. Has had a prior anti-cancer monoclonal antibody (mAb) within 4 weeks prior to study Day 1 or who has not recovered (i.e.,  $\leq$  Grade 2 or at baseline) from adverse events due to agents administered more than 4 weeks earlier.
6. Has had prior chemotherapy within 2 weeks prior to study Day 1 or who has not recovered (i.e.,  $\leq$  Grade 2 or at baseline) from adverse events due to a previously administered agent and meeting the criteria for organ function described in section 4.1.7 Patients who receive palliative radiation therapy within 1 week prior to day 1 are allowed. Patients on treatment with targeted therapy (like EGFR or ALK TKIs) may start study treatment 5 days from last treatment.  
Note: Subjects with  $\leq$  Grade 2 neuropathy or other clinically insignificant AEs as determined by the PI are an exception to this criterion and may qualify for the study following adequate pre-study documentation.  
Note: If subject received major surgery, they must have recovered adequately from the toxicity and/or complications from the intervention prior to starting therapy.
7. Receiving other investigational agent concomitantly.

8. Has a known additional malignancy that is progressing or requires active treatment. Exceptions include superficial skin cancers that are surgically removed without need for systemic therapy, in situ cervical cancer, superficial bladder cancer or localized low grade prostate cancer not requiring active treatment.
9. Has active or documented history of autoimmune disease that has required systemic treatment in the preceding 2 years (i.e. required use of disease modifying agents such as corticosteroids or other immunosuppressive drugs). Patients with psoriasis and rheumatoid arthritis with no evidence of disease flare off immunosuppression for >1 year may be allowed after discussion with the study PI. Replacement therapy (eg., thyroxine, insulin, or physiologic corticosteroid replacement therapy for adrenal or pituitary insufficiency, etc.) is not considered a form of systemic treatment.
10. Has known history of, or any evidence of active, non-infectious pneumonitis.
11. Has an active infection requiring systemic therapy.
12. Has a history or current evidence of any condition, therapy, or laboratory abnormality that might confound the results of the trial, interfere with the subject's participation for the full duration of the trial, or is not in the best interest of the subject to participate, in the opinion of the treating investigator.
13. Has known psychiatric or substance abuse disorders that would interfere with cooperation with the requirements of the trial.
14. Is pregnant or breastfeeding, or expecting to conceive or father children within the projected duration of the trial, starting with the pre-screening or screening visit through 217 days after the last dose of trial treatment. Women of childbearing potential (WOCBP)\* should agree to methods of contraception described in the protocol.

\* WOCBP is defined as any female who has experienced menarche and who has not undergone surgical sterilization (hysterectomy or bilateral oophorectomy) or who is not postmenopausal. Menopause is defined clinically as 12 months of amenorrhea in a woman over 45 in the absence of other biological or physiological causes. In addition, women under the age of 62 must have a documented serum follicle stimulating hormone (FSH) level >40 mIU/mL.

Women of childbearing potential (WOCBP) receiving nivolumab will be instructed to adhere to contraception for a period of 23 weeks after the last dose of investigational product. Men receiving nivolumab and who are sexually active with WOCBP will be instructed to adhere to contraception for a period of 31 weeks after the last dose of investigational product. These durations have been calculated using the upper limit of the half-life for nivolumab (25 days) and are based on the protocol requirement that WOCBP use contraception for

5 half-lives plus 30 days and men who are sexually active with WOCBP use contraception for 5 half-lives plus 90 days.

